10.3. Vital Sign Measurements and Body Weight

Vital sign measurements will be performed at Screening, on Day –1, on Day 1 prior to the start of study drug administration (within 30 minutes), on Days 2 (at 24 hours after injection), 3, 8, 15, 29, 43, and 57, and at EOS.

Vital signs measurements will include systolic and diastolic BPs, heart rate, respiratory rate, and body temperature. Blood pressure and heart rate measurements will be performed after the subject has been resting for at least 5 minutes.

Actual values and change from Baseline for systolic and diastolic BPs, heart rate, respiratory rate, and body temperature will be summarized by treatment arm and overall at each time point using descriptive statistics (n, mean, SD, minimum, median, and maximum) for the safety population.

Individual vital sign measurements (including repeated and unscheduled measurements) will be presented in a data listing for the safety population.

Body weight will be measured at Screening, on Day –1, and at EOS. All body weight data will be presented in a data listing for the safety population.

10.4. Electrocardiogram

Single 12-lead ECGs will be obtained after the subject has been in the supine position for at least 5 minutes at Screening and at EOS.

The investigator will determine whether any of the 12-lead ECG results are clinically significant or not clinically significant. Findings of 12-lead ECG will be classified as either “normal”, “abnormal, not clinically significant”, or “abnormal, clinically significant”.

The shift from baseline of categorical investigator interpretation will be summarized at each visit by treatment arm and overall for the safety population.

The investigator’s interpretation, including hypersensitivity/allergic reactions monitoring, will be presented in a data listing for the safety population.

10.5. Hypersensitivity/Allergic Reactions Monitoring

Hypersensitivity/allergic reactions will be assessed by additional ECG and vital sign monitoring (including systolic and diastolic BP, heart rate, respiratory rate, and body temperature).

Vital sign measurements for hypersensitivity/allergic reactions monitoring will be performed on Day 1 (prior to start of study drug administration [within 15 minutes], at 3 hours [\pm 30 minutes], 6 hours [\pm 30 minutes], and 12 hours [\pm 60 minutes] after injection) and on Day 2 at 24 hours (\pm 60 minutes) after injection. On Day 1 (pre-dose) and Day 2, the vital signs measurement may be considered as a part of hypersensitivity monitoring and only either one will be recorded in the eCRF.

Electrocardiograms for hypersensitivity/allergic reactions monitoring will be performed at 3 hours (± 30 minutes) after the administration of study drug and additional ECGs can be performed if the subject experiences cardiac symptoms.

In addition, hypersensitivity/allergic reactions will be monitored by routine continuous clinical monitoring. In case of hypersensitivity, emergency medication and equipment, such as adrenaline, antihistamines, corticosteroids, and respiratory support including inhalational therapy, oxygen, and artificial ventilation, will be available and an ECG can be performed.

Actual values and changes from Baseline for hypersensitivity/allergic reactions monitoring will be summarized separately for vital sign measurements by treatment arm and overall at each time point using descriptive statistics (n, mean, SD, minimum, median, and maximum) for the safety population.

The number and percentage of subjects who have clinically notable hypersensitivity/allergic reactions vital sign measurements will be summarized in a table by treatment arm and overall, time point, and parameter for the safety population. The criteria for clinically notable results are defined as below.

Parameter	Low	High
Systolic blood pressure (mmHg)	≤ 90	≥ 160
Diastolic blood pressure (mmHg)	≤ 50	≥ 90
Respiratory rate (breaths per minute)	≤ 12	≥ 20
Heart rate (beats per minute)	≤ 50	≥ 100
Body temperature ($^{\circ}\text{C}$)	≤ 35.0	≥ 38.0

A shift table comparing the categorical investigator interpretation of ECGs at 3 hours after the administration of study drug on Day 1 with those at Baseline will be summarized by treatment arm and overall for the safety population.

Hypersensitivity/allergic reactions monitoring for vital sign measurements (including repeated assessment) will be listed in a data listing for the safety population. High and low flags will be included to show whether a hypersensitivity/allergic reaction result is outside of the clinically notable ranges.

Hypersensitivity/allergic reactions monitoring for ECG assessments will be listed within ECG listing as described in [Section 10.4](#).

10.6. Physical Examination

A standard physical examination will be performed at Screening, on Day -1, on Day 3, and at EOS. The examination will include an assessment of general appearance and a review of systems.

All physical examination findings will be presented in a data listing for the safety population. A shift table comparing the categorical results at each scheduled post-baseline visit with those at Baseline will be summarized by treatment arm and overall for the safety population.

10.7. Tuberculosis Assessments

A chest X-ray (both posterior–anterior and lateral views), IGRA, and signs and symptoms of TB clinical monitoring will be performed at Screening. Subjects will be monitored for the clinical signs and symptoms of TB throughout the study and until the EOS. Additional chest X-ray and IGRA testing will be performed at the investigator’s discretion based on the judgment on the signs and symptoms of TB monitoring throughout the study and until the EOS. Only IGRA will be performed at the EOS visit.

Results of IGRA will be summarized in a table by treatment arm and overall for the safety population.

Chest X-ray, TB monitoring, and IGRA test results will be presented in data listings for the safety population.

10.8. Pregnancy Test

A serum pregnancy test will be performed at Screening and the EOS visit. A urine pregnancy test will be performed in women of childbearing potential on Day -1. Throughout the study, a urine pregnancy test will be performed when there is any possibility of pregnancy, and a confirmatory serum pregnancy test will be performed if a urine pregnancy test result is positive.

The pregnancy test results will be summarized for female subjects of childbearing potential in the safety population. All pregnancy test results will be presented in a data listing.

10.9. Local Site Pain

Local site pain will be assessed immediately (within 15 minutes) after study drug administration (Day 1) using 100 mm VAS. Subjects will be asked to indicate their current level of pain intensity by drawing a single vertical line on the 100 mm VAS labeled “no pain” (0 mm) as the left anchor and “most severe pain” (100 mm) as the right anchor. The length of the line will be measured from the left (in mm) and the value (in mm) will be recorded in the eCRF.

Individual VAS results will be presented in a data listing for the safety population. The VAS results will be summarized by treatment arm and overall for the safety population.

In the primary PK analysis, the body weight as measured on Day -1 will be included in covariates instead of the stratification level of body weight (≥ 80 kg vs. < 80 kg).

13. References

eCRF: A Phase 1, Randomized, Double-blind, Three-arm, Parallel group, Single-dose Study to Compare the Pharmacokinetics and Safety of CT-P17 and Humira (US-licensed Humira and EU-approved Humira) in Healthy Subjects, Version 6.0, 06 November 2019.

Protocol: A Phase 1, Randomized, Double-blind, Three-arm, Parallel group, Single-dose Study to Compare the Pharmacokinetics and Safety of CT-P17 and Humira (US-licensed Humira and EU-approved Humira) in Healthy Subjects, Version 2.1 08 January 2019.

14. Appendices

14.1. Schedule of Study Procedures

	Screening ¹	Study Period ²																	EOS ³
Study day (Visit windows)	-28 to -2	-1	1	2	3	4	5	5.5	6	6.5	7	8	9	15	22	29	43	57	71
Procedure																			
Informed consent	X																		
Medical history	X	X																	
Demographics	X																		
Inclusion / exclusion criteria ⁴	X	X																	
Body weight & height ⁵	X	X																	X
Physical examination	X	X			X														X
Hepatitis B/C, HIV and syphilis test ⁶	X																		
TB screening (chest X-ray and IGRA) ⁷	X																		(X)
Serum pregnancy test ⁸	X																		X
Urine pregnancy test ⁸			X																
Urine drug abuse / alcohol / cotinine check ⁹	X	X																	
Randomization			X																
Clinical laboratory tests ¹⁰	X	X			X							X		X		X	X	X	X
Vital signs ¹¹	X	X	X	X	X							X		X		X	X	X	X
12-Lead ECG	X																		X
Administration of study drug¹²			X																
Pharmacokinetic sampling ¹³			X	X	X	X	X	X	X	X	X	X	X	X	X	X	X	X	X
Immunogenicity sampling ¹⁴			X												X		X		X
Hypersensitivity monitoring ¹⁵			X	X															
Injection site reaction ¹⁶			X																
VAS local site pain ¹⁷			X																
Prior, concomitant medications ¹⁸														X					
Adverse events ¹⁹														X					
TB clinical monitoring ⁷														X					

Abbreviations: ECG, electrocardiogram; EOS, End-of-Study; HIV, human immunodeficiency virus; IGRA, interferon- γ release assay; TB, tuberculosis; VAS, visual analogue scale.

1. During the screening period, retest for screening is permitted only once by the Investigator's judgment. If the repeated test result is again not suitable or indeterminate for inclusion, the subject will be screen failed.
2. Subjects will be confined to the study center until completion of the 48-hour assessments after the administration of the study drug (Day 1) and admission can be extended depending on the subject's and study center's availability, up to Day 7. The consecutive study visits will be carried out on an out-patient basis.
3. All EOS assessments will be performed on Day 71, for all subjects including those who discontinued prematurely.
4. Inclusion and exclusion criteria should be confirmed before Day -1. On the Day -1, recheck process will be performed.
5. Height will be measured at Screening only.
6. Serology tests will be performed at the Screening visit for anti-HIV (HIV-1 and HIV-2) antibodies, hepatitis B surface antigen (HBsAg), hepatitis B surface antibody (HBsAb), hepatitis B core antibody (HBcAb [total or IgG]), HBV DNA (if subject has HBsAg negative, HBsAb negative or positive, and HBcAb positive), hepatitis C antibody (HCAb), and nontreponemal (e.g., Rapid Plasma Reagins) tests.
7. At Screening, a chest X-ray, an IGRA, and signs and symptoms of TB clinical monitoring will be performed. If the result of IGRA is indeterminate at Screening, a retest will be allowed only once during the Screening period. Additional IGRA test and chest X-ray will be performed if symptoms raise a suspicion of TB upon the judgement of the investigator during the study and until the EOS. Only IGRA will be performed at the EOS visit; signs and symptoms of TB clinical monitoring will be performed throughout the study and until the EOS.
8. A serum pregnancy test on women of childbearing potential will be performed at Screening and the EOS visit. A urine pregnancy test will be performed in women of childbearing potential on Day -1. Throughout the study, a urine pregnancy test will be performed when there is any possibility of pregnancy, and a confirmatory serum pregnancy test will be performed if a urine pregnancy test result is positive.
9. Urine drug screen (tetrahydrocannabinol, opiates, cocaine, methamphetamine, barbiturates and benzodiazepines) and history check by the investigator will be performed for drug abuse, alcohol, and cotinine check in Screening and Day -1.
10. Clinical laboratory tests will be carried out: **Hematology** (hematocrit, hemoglobin, red blood cell count, white blood cell count with differential, absolute neutrophil count, platelets), **Serum chemistry** (albumin, alkaline phosphatase, alanine aminotransferase, aspartate aminotransferase, blood urea nitrogen, calcium, chloride, total cholesterol, creatine phosphokinase, creatinine, creatine kinase-myocardial band isoenzyme [CK-MB], creatinine clearance [estimated by Modification of Diet in Renal Disease formula], C-reactive protein, gamma-glutamyl transferase, glucose, lactate dehydrogenase, magnesium, potassium, sodium, total bilirubin, total protein, uric acid, direct bilirubin, triglycerides, inorganic phosphorus, high-density lipoprotein cholesterol, Troponin I), **Urinalysis** (color, pH, specific gravity, ketones, protein, glucose, bilirubin, nitrite, urobilinogen, occult blood, and microscopic examination). Creatinine clearance will be calculated using serum creatinine level only at screening for inclusion.
11. Vital sign measurement on Day 1 will be performed before the start of the study drug administration (within 30 minutes). Additional vital signs will be measured after the study drug administration. On Day 1 (pre-dose) and Day 2, the vital signs measurement may be considered as a part of hypersensitivity monitoring and only either one will be recorded in the eCRF.
12. The study drug will be administered on the subject's lower abdomen except for the 5 cm around the subject's navel.
13. Samples for pharmacokinetic analysis will be obtained at the following time points:

PK sampling time points
Day 1 Pre-dose (within 60 minutes prior to administration of the study drug)
Day 1 (6 hours after the administration of the study drug); \pm 15 minutes
Day 1 (12 hours after the administration of the study drug); \pm 1 hour
Day 2 (24 hours after the administration of the study drug); \pm 2 hours

Day 3, 4, 5, 5.5, 6, 6.5, 7, 8, and 9 (48, 72, 96, 108, 120, 132, 144, 168, and 192 hours, respectively, after the administration of the study drug); ± 2 hours
Day 15 and 22 (336 and 504 hours, respectively, after the administration of the study drug); ± 4 hours
Day 29, 43, 57, and 71 (i.e., EOS) after the administration of the study drug; ± 1 day

14. Sample for immunogenicity analysis on Day 1 will be performed prior to the study drug administration.
15. For hypersensitivity monitoring, vital sign measurements will be performed before the start of the study drug administration (within 15 minutes) and at 3, 6, 12, and 24 hours after injection on Day 1. The tolerance window is ± 30 minutes for 3 and 6 hours, and ± 60 minutes for 12 and 24 hours after the administration. Either 3-lead or 12-lead ECG can be used for hypersensitivity monitoring at 3 hours (± 30 minutes) after the administration of the study drug on Day 1 and additional ECG will be performed if a subject experiences cardiac symptoms. Emergency equipment, such as adrenaline, antihistamines, corticosteroids, and respiratory support (inhalational therapy, oxygen and artificial ventilator) must be available.
16. Injection site reaction will be assessed 30 minutes (± 10 minutes) after the study drug administration.
17. Local site pain will be observed using VAS immediately (within 15 minutes) after the study drug administration.
18. Use of all prior and concomitant medications, from within 30 days prior to the administration of the study drug (Day 1) until the last assessment date or EOS visit, will be recorded.
19. Adverse events (and serious adverse events) should be reported until the end of the subject's participation in the study, regardless of the relationship to the study drug.

14.2. CTCAE v5.0 for Clinical Laboratory Test Results

CTCAE Term	Laboratory Parameter	Level	Grade 1	Grade 2	Grade 3	Grade 4
Anemia	Hemoglobin	Low	<LLN - 10.0 g/dL; <LLN - 100 g/L; <LLN - 6.2 mmol/L	<10.0 - 8.0 g/dL; <6.2 - 4.9 mmol/L; <100 - 80 g/L	<8.0 g/dL; <4.9 mmol/L; <80 g/L	-
Alanine aminotransferase increased	ALT	High	>ULN - 3.0 x ULN if baseline was normal; 1.5 - 3.0 x baseline if baseline was abnormal	>3.0 - 5.0 x ULN if baseline was normal; >3.0 - 5.0 x baseline if baseline was abnormal	>5.0 - 20.0 x ULN if baseline was normal; >5.0 - 20.0 x baseline if baseline was abnormal	>20.0 x ULN if baseline was normal; >20.0 x baseline if baseline was abnormal
Alkaline phosphatase increased	ALP	High	>ULN - 2.5 x ULN if baseline was normal; 2.0 - 2.5 x baseline if baseline was abnormal	>2.5 - 5.0 x ULN if baseline was normal; >2.5 - 5.0 x baseline if baseline was abnormal	>5.0 - 20.0 x ULN if baseline was normal; >5.0 - 20.0 x baseline if baseline was abnormal	>20.0 x ULN if baseline was normal; >20.0 x baseline if baseline was abnormal
Aspartate aminotransferase increased	AST	High	>ULN - 3.0 x ULN if baseline was normal; 1.5 - 3.0 x baseline if baseline was abnormal	>3.0 - 5.0 x ULN if baseline was normal; >3.0 - 5.0 x baseline if baseline was abnormal	>5.0 - 20.0 x ULN if baseline was normal; >5.0 - 20.0 x baseline if baseline was abnormal	>20.0 x ULN if baseline was normal; >20.0 x baseline if baseline was abnormal
Blood bilirubin increased	Total Bilirubin	High	>ULN - 1.5 x ULN if baseline was normal; > 1.0 - 1.5 x baseline if baseline was abnormal	>1.5 - 3.0 x ULN if baseline was normal; >1.5 - 3.0 x baseline if baseline was abnormal	>3.0 - 10.0 x ULN if baseline was normal; >3.0 - 10.0 x baseline if baseline was abnormal	>10.0 x ULN if baseline was normal; >10.0 x baseline if baseline was abnormal
Blood lactate dehydrogenase increased	LDH	High	>ULN			
Cholesterol high	Total Cholesterol	High	>ULN - 300 mg/dL; >ULN - 7.75 mmol/L	>300 - 400 mg/dL; >7.75 - 10.34 mmol/L	>400 - 500 mg/dL; >10.34 - 12.92 mmol/L	>500 mg/dL; >12.92 mmol/L

CPK increased	CPK	High	>ULN - 2.5 x ULN	>2.5 x ULN - 5 x ULN	>5 x ULN - 10 x ULN	>10 x ULN
Creatinine increased	Creatinine	High	>ULN - 1.5 x ULN	>1.5 - 3.0 x baseline; >1.5 - 3.0 x ULN	>3.0 x baseline; >3.0 - 6.0 x ULN	>6.0 x ULN
Eosinophilia	Eosinophils	High	>ULN and >Baseline			
GGT increased	GGT	High	>ULN - 2.5 x ULN if baseline was normal; 2.0 - 2.5 x baseline if baseline was abnormal	>2.5 - 5.0 x ULN if baseline was normal; >2.5 - 5.0 x baseline if baseline was abnormal	>5.0 - 20.0 x ULN if baseline was normal; >5.0 - 20.0 x baseline if baseline was abnormal	>20.0 x ULN if baseline was normal; >20.0 x baseline if baseline was abnormal
Hemoglobin increased	Hemoglobin	High	Increase in >0 - 2 g/dL	Increase in >2 - 4 g/dL	Increase in >4 g/dL	-
Hyperkalemia	Potassium	High	>ULN - 5.5 mmol/L	>5.5 - 6.0 mmol/L	>6.0 - 7.0 mmol/L	>7.0 mmol/L
Hypermagnesemia	Magnesium	High	>ULN - 3.0 mg/dL; >ULN - 1.23 mmol/L		>3.0 - 8.0 mg/dL; >1.23 - 3.30 mmol/L	>8.0 mg/dL; >3.30 mmol/L
Hypernatremia	Sodium	High	>ULN - 150 mmol/L	>150 - 155 mmol/L	>155 - 160 mmol/L;	>160 mmol/L
Hypertriglyceridemia	Triglyceride	High	150 mg/dL - 300 mg/dL; 1.71 mmol/L - 3.42 mmol/L	>300 mg/dL - 500 mg/dL; >3.42 mmol/L - 5.7 mmol/L	>500 mg/dL - 1,000 mg/dL; >5.7 mmol/L - 11.4 mmol/L	>1,000 mg/dL; >11.4 mmol/L
Hyperuricemia	Uric acid	High	>ULN			
Hypoalbuminemia	Albumin	Low	<LLN - 3 g/dL; <LLN - 30 g/L	<3 - 2 g/dL; <30 - 20 g/L	<2 g/dL; <20 g/L	-
Hypoglycemia	Glucose	Low	<LLN - 55 mg/dL; <LLN - 3.0 mmol / L	< 55 - 40 mg/dL; < 3.0 - 2.2 mmol / L	< 40 - 30 mg/dL; < 2.2 - 1.7 mmol / L	<30 mg/dL; <1.7 mmol/L
Hypokalemia	Potassium	Low	<LLN - 3.0 mmol/L		<3.0 - 2.5 mmol/L	<2.5 mmol/L
Hypomagnesemia	Magnesium	Low	<LLN - 1.2 mg/dL; <LLN - 0.5 mmol/L	<1.2 - 0.9 mg/dL; <0.5 - 0.4 mmol/L	<0.9 - 0.7 mg/dL; <0.4 - 0.3 mmol/L	<0.7 mg/dL; <0.3 mmol/L

Hyponatremia	Sodium	Low	<LLN - 130 mmol/L	125-129 mmol/L	120-124 mmol/L regardless of symptoms	<120 mmol/L
Leukocytosis	Blood WBC	High			>100,000/mm ³	
Lymphocyte count decreased	Lymphocytes	Low	<LLN - 800/mm ³ ; <LLN - 0.8 x 10 ⁹ /L	<800 - 500/mm ³ ; <0.8 - 0.5 x 10 ⁹ /L	<500 - 200/mm ³ ; <0.5 - 0.2 x 10 ⁹ /L	<200/mm ³ ; <0.2 x 10 ⁹ /L
Lymphocyte count increased	Lymphocytes	High	-	>4,000/mm ³ - 20,000/mm ³	>20,000/mm ³	-
Neutrophil count decreased	Total Neutrophils	Low	<LLN - 1,500/mm ³ ; <LLN - 1.5 x 10 ⁹ /L	<1500 - 1,000/mm ³ ; <1.5 - 1.0 x 10 ⁹ /L	<1,000 - 500/mm ³ ; <1.0 - 0.5 x 10 ⁹ /L	<500/mm ³ ; <0.5 x 10 ⁹ /L
Platelet count decreased	Platelet count	Low	<LLN - 75,000/mm ³ ; <LLN - 75.0 x 10 ⁹ /L	<75,000 - 50,000/mm ³ ; <75.0 - 50.0 x 10 ⁹ /L	<50,000 - 25,000/mm ³ ; <50.0 - 25.0 x 10 ⁹ /L	<25,000/mm ³ ; <25.0 x 10 ⁹ /L
White blood cell decreased	Blood WBC	Low	<LLN - 3,000/mm ³ ; <LLN - 3.0 x 10 ⁹ /L	<3,000 - 2,000/mm ³ ; <3.0 - 2.0 x 10 ⁹ /L	<2,000 - 1,000/mm ³ ; <2.0 - 1.0 x 10 ⁹ /L	<1,000/mm ³ ; <1.0 x 10 ⁹ /L

Note: LLN = lower limit of normal, ULN = upper limit of normal. The LLN and ULN values will be the lower and upper limits of the normal ranges as provided by the local laboratory. Semicolon (;) indicates “or”.

CTCAE = Common Terminology Criteria for Adverse Events, ALT = alanine aminotransferase, ALP = alkaline phosphatase, AST = aspartate aminotransferase, LDH = lactate dehydrogenase, CPK = creatine phosphokinase, GGT = gamma glutamyl transferase, WBC= white blood cell.

In case of numeric value for grading is identical such as Hypokalemia and Hyperuricemia, CTCAE grade which includes numeric value only was applied, because abnormal laboratory value with clinical input was reported as an adverse event and graded accordingly.

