Abnormal clinical laboratory values will be flagged as either high or low or abnormal based on the reference ranges provided by the local laboratories for each laboratory parameter. The investigator will determine whether any of the abnormal clinical laboratory values are clinically significant or not clinically significant.

Clinical laboratory test results will be labeled with a CTCAE term, and grading will be applied to post-baseline values for numeric parameters based on CTCAE v5.0 where applicable. Grades which are part numeric and part clinical input will be assigned based on the numeric portion only; lower grade will be used if different grades share the same criteria. The criteria are listed in [Appendix 14.2](#). Unit conversion will be performed if the clinical laboratory unit is not consistent with unit in CTCAE v5.0, however it will be the CTCAE criteria unit that is converted as all laboratory findings will be reported in the SI units.

Actual values and changes from Baseline for quantitative clinical laboratory test results (hematology, serum chemistry, and urinalysis) will be summarized by treatment arm and overall at each time point using descriptive statistics (n, mean, SD, minimum, median, and maximum) for the safety population. Shift tables from baseline to each schedule post-baseline visit, will be generated for clinical laboratory test results (hematology, serum chemistry, and urinalysis) using normal; abnormal, clinically significant; abnormal, not clinically significant categories as appropriate, by treatment arm and overall for the safety population.

The number and percentage of subjects will be summarized by CTCAE term, CTCAE grade, and treatment arms and overall for the safety population, where this summary includes only the most severe case during the overall visits. The CTCAE terms and ranges for applicable parameters are listed in [Appendix 14.2](#). The CTCAE grades for this analysis will be Grade 1 (Mild), Grade 2 (Moderate), Grade 3 (Severe) and Grade 4 (Life-threatening). The CTCAE Grade 5 (Death) will not be applied in this analysis since death cannot be determined from a numeric laboratory result. If a subject's most severe result does not satisfy any CTCAE criteria, this subject will be summarized as "No Grade".

Absolute lymphocyte and absolute eosinophil will be calculated as follows:

- Absolute lymphocyte count ($10^9/L$) = [WBC ($10^9/L$) * Lymphocytes (Proportion of 1.0)].

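### SAP 14.2 grades five liver-test rows against baseline when baseline was abnormal, without limiting this to values above ULN, so a within-range result after a low baseline can be tabulated as increased

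*SAP*

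**What the plan says.** SAP 14.2 lists the numeric criteria used to grade post-baseline laboratory values. Five rows (ALT, ALP, AST, total bilirubin, GGT) have two branches. If baseline was normal, the cut-points are multiples of ULN. If baseline was abnormal, they are multiples of the subject's own baseline:

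- Total bilirubin: Grade 1 is "> 1.0 - 1.5 x baseline if baseline was abnormal", Grade 2 is ">1.5 - 3.0 x baseline if baseline was abnormal" and Grade 3 is ">3.0 - 10.0 x baseline if baseline was abnormal".
- ALT and AST: Grade 1 is "1.5 - 3.0 x baseline if baseline was abnormal" and Grade 2 is ">3.0 - 5.0 x baseline if baseline was abnormal"; Grade 3 starts above 5.0 x baseline.
- ALP and GGT: Grade 1 is "2.0 - 2.5 x baseline if baseline was abnormal"; Grade 2 starts above 2.5 x and Grade 3 above 5.0 x baseline.

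The notes under the table define LLN and ULN as the local laboratory's limits. They do not define an abnormal baseline. SAP 10.2 states: "Abnormal clinical laboratory values will be flagged as either high or low or abnormal based on the reference ranges". Its shift-table categories (normal, or abnormal with or without clinical significance) also carry no direction. The grade table counts subjects by term and grade, "where this summary includes only the most severe case during the overall visits". Baseline is the last non-missing value before dosing (SAP 5.2).

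**The concern.** The baseline branch makes sense for a subject who starts above ULN, because a multiple of ULN would then grade a value that has not risen. It does not make sense for a subject who starts below LLN: a return to the middle of the normal range is a large multiple of a small number.

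Nothing in the plan keeps such subjects off the branch. Protocol 4.1 caps ALT, AST and bilirubin from above only and gives no numeric limit for ALP or GGT. Under Protocol 6.2.4 a screening abnormality bars entry without sponsor permission only if it is clinically significant, which a slightly low enzyme or bilirubin need not be.

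At stake is how the laboratory grade table reads. It keeps each subject's worst grade over seven post-dose laboratory visits (Days 3, 8, 15, 29, 43, 57 and EOS), in healthy volunteers compared across three arms. A few liver-test entries at Grade 2 or 3 would draw attention there, and some could be normal results.

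**Working it through.** The plan states no figure to reproduce; the check applies the rule as written.

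**Step 1. Which branch does a low baseline take?** SAP 14.2 offers only normal and abnormal. A value below LLN is not normal. By the usage in SAP 10.2 it is abnormal. It therefore takes the baseline multiples.

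**Step 2. Is there a ULN condition on the graded value?** Not in the baseline branches of these five rows. Elsewhere in the same table the LDH row requires a value above ULN, and the eosinophilia row requires a value above both ULN and baseline.

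**Step 3. Highest grade open to a value at or below ULN.** Let R = ULN / baseline, with baseline below LLN. The largest in-range multiple of baseline is R, so the cut-points in SAP 14.2 give:

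| Row | Grade 1 if | Grade 2 if | Grade 3 if | Grade 4 if |
|---|---|---|---|---|
| Total bilirubin | R > 1 | R > 1.5 | R > 3 | R > 10 |
| ALT, AST | R ≥ 1.5 | R > 3 | R > 5 | R > 20 |
| ALP, GGT | R ≥ 2 | R > 2.5 | R > 5 | R > 20 |

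Since baseline is below ULN, R > 1 always holds, so for bilirubin any rise above a low baseline is at least Grade 1.

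**Step 4. Illustrations.** The documents give no reference limits, so the ranges and baselines below are assumptions.

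| Analyte (assumed range) | Assumed baseline | R | In-range values graded as increased |
|---|---|---|---|
| Bilirubin (3.4–20.5 µmol/L) | 3.0 | 20.5/3.0 = 6.83 | up to 4.5 Grade 1; >4.5–9.0 Grade 2; >9.0–20.5 Grade 3 |
| ALT (7–40 U/L) | 6 | 40/6 = 6.67 | 9–18 Grade 1; >18–30 Grade 2; >30–40 Grade 3 |
| GGT (8–60) | 7 | 60/7 = 8.57 | 14–17.5 Grade 1; >17.5–35 Grade 2; >35–60 Grade 3 |
| AST (10–40) | 9 | 40/9 = 4.44 | 13.5–27 Grade 1; >27–40 Grade 2; Grade 3 would need >45 |
| ALP (40–120) | 36 | 120/36 = 3.33 | 72–90 Grade 1; >90–120 Grade 2; Grade 3 would need >180 |

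Under these ranges every normal bilirubin is graded after a baseline of 3.0. In-range Grade 3 is reachable for bilirubin, ALT and GGT, but not for AST or ALP.

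**Step 5. The rule with the baseline branch limited to baseline above ULN.** If baseline is at or below ULN, the ULN multiples apply and only a value above ULN is graded. If baseline is above ULN and the later value is at or below ULN, the multiple is below 1, and no row grades a multiple of 1 or less. So no value at or below ULN is graded in these five rows. Grades for normal or high baselines do not change.

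**The case against.** **The SAP never says that abnormal includes low.** This is correct. The sentence in SAP 10.2 concerns flags, and it lists abnormal as a flag beside high and low, so it does not cleanly define the word for 14.2. All five rows have level High and a term meaning increased, and a programmer could reasonably read an abnormal baseline in that direction. A reader might infer from 10.2 that the SAP defines a low baseline as abnormal for grading; the documents do not go that far. What stands is that the literal reading leads to the baseline branch and no text rules it out. On the directional reading, a below-LLN baseline is strictly neither normal nor abnormal and has no stated branch. Either way the rule needs a definition.

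**The wording may be that of CTCAE v5.0.** SAP 10.2 and the title of 14.2 present the table as that scale, and the source cannot be checked from these documents. This affects how the fix is framed: it should be a declared interpretation, not a silent rewording.

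**Other outputs would expose the artefact, and it favours no arm.** SAP 10.2 also provides high and low flags, values and changes by visit, shift tables and listings. Adverse event severity is graded separately. Baseline precedes dosing and allocation is randomised, so no systematic bias between arms is expected. All of this stands and limits the consequence. It does not correct the grade table.

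**Other rows also lack a ULN condition.** The increased-hemoglobin row and the baseline multiples for creatinine can grade normal values too. This is true, but it is a separate matter that the change below does not address.

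**Conclusion.** The point holds as an undefined condition whose literal reading gives misleading entries. In the five rows, a subject whose baseline is below LLN can be tabulated as having an increased result while at or below ULN.

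Two stronger statements are tempting, and the documents do not support them:

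- A reader might infer that normal values can reach Grade 3 in all five rows. That requires ULN above 3 x baseline for bilirubin and above 5 x baseline for the other four. The local limits are not given, and under the ranges assumed here AST and ALP stop at Grade 2.
- A reader might put a number on the subjects affected. If every local range were a central 95% interval and the trial population filled its lower tail, 306 x 0.025 = 7.7, or about 8 subjects per analyte, would start low. Neither assumption is in the documents, and the figure is zero where a laboratory sets no lower limit. The count cannot be derived.

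The effect is confined to the descriptive worst-grade CTCAE laboratory table. No test, margin or decision depends on it, and neither the PK comparison nor investigator-graded adverse events are touched. It is worth correcting because a liver-test grade table in healthy subjects should not need its listings to be read correctly.

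**What to change.** Add a note to SAP 14.2: for the ALT, ALP, AST, total bilirubin and GGT rows, an abnormal baseline means a baseline above ULN, and the ULN multiples apply to every other baseline, including one below LLN. State that this is the SAP's programming interpretation of the CTCAE v5.0 wording, so that any departure from the named scale is visible.

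The cost is one note and one programming condition. If the change is made after database lock, SAP section 2 requires the resulting table to be labelled post-hoc.
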